12.4 ADVERSE EVENTS (AE'S) AND TREATMENT EMERGENT ADVERSE EVENTS (TEAE'S)

All AEs and SAEs occurring on study will be listed by patient. The frequency and percentages of patients with treatment-emergent adverse events (TEAEs) will be tabulated by system organ class (SOC) and preferred term (PT), where treatment-emergent is defined as any AE that:

- Occurs after first dosing of study medication and through the end of the study or up through 30 days after the last dose of study treatment, or
- Is considered treatment-related regardless of the start date of the event, or
- Is present before first dosing of study medication but worsens in intensity or the investigator subsequently considers treatment-related.

TEAEs that are considered at least possibly related to study treatment will be tabulated as well as deaths, SAEs, and events resulting in treatment discontinuation.

AEs that occur after informed consent but before first dosing of study medication will not be summarized but will be listed.

At each level of summarization, a patient will be counted only once for each AE, SOC, or PT experienced within that level. In the summation for AE severity, within each level of AE, SOC, or PT experienced, the one with the highest severity will be included. In the summation for AE's relationship to the study drug, within each level of AE, SOC, or PT experienced, the one with the closest relationship to the study drug will be included.

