8 ADVERSE EVENTS

Each AE and SAE term recorded on the case report forms (CRFs) will be mapped to a preferred term (PT) using the MedDRA dictionary. The investigator will classify the severity of AEs and SAEs using the NCI CTCAE v4.0 and will assess the relationship of each event to study treatment.

All AEs and SAEs occurring on study will be listed by treatment drug, center, and patient. The frequency and percentages of patients with treatment-emergent adverse events (TEAEs) will be tabulated by system organ class (SOC) and PT, where treatment-emergent is defined as any AE that;

- occurs on or after Cycle 1/Day 1 and through the end of the study or, if serious, up through 30 days after the last dose of study treatment;
- is present before Cycle 1/Day 1 but worsens in intensity or the investigator subsequently considers treatment-related.

For the purpose of calculating treatment emergence and inclusion in summary tables, incomplete onset dates will be imputed as detailed in Appendix A – Imputation Rules for Missing Data. Summaries will display incidence by study drug received and total incidence, and PTs within each SOC will appear in decreasing order of total incidence as well as in alphabetical order. At each level of summarization, a patient will be counted only once for each AE, SOC, or PT experienced within that level.

Related TEAEs, serious TEAEs, Grade 3 or higher TEAEs, related serious TEAEs, related Grade 3 or higher TEAEs, and TEAEs resulting in discontinuation of study treatment will be similarly summarized. Summaries of TEAEs by relationship to the study treatment will also be prepared.

At each level of summarization, a patient will be counted only once for each AE, SOC, or PT experienced within that level. In the summation for AE severity, within each level of AE, SOC, or PT experienced, the one with the highest severity will be included. In the summation for AE's relationship to the study drug, within each level of AE, SOC, or PT experienced, the one with the closest relationship to the study drug will be included.

AEs will be summarized for the treatment that the patient last receives prior to the occurrence of the AEs.

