12 APPENDIX A - IMPUTATION RULES FOR MISSING DATA

Terminology in this appendix: first dose = first administration of any study treatment

The date of event (death/progression) is the documented date of event.

The missing date will be handled as follows:

What is	s missing in event date	Imputed value is
Year		
•	If month is missing or cannot be confirmed to be earlier than the month of last assessment	the year of last assessment
•	If, without considering year, the date of the event is confirmed to be earlier than the date of the last assessment (e.g., January vs November or May 15 vs May 1)	the year of last assessment+1
Month		
•	If year of the event is missing or is confirmed to be the same as the year of the last assessment	Month of the last assessment unless the day of death is earlier than the day of the last assessment (5th vs. 10th). In this case the month will be imputed as the month after the month of the last assessment
•	If year of the event is confirmed to be after the year of the last assessment	January
Day		1, unless the resulting imputed date is earlier than the last assessment date. In this case the imputed day is the day of the last assessment

Adverse Event

- If onset date is completely missing, onset date is set to date of first dose.
- If (year is present and month and day are missing) or (year and day are present and month is missing):
 - o If year = year of first dose, then set month and day to month and day of first dose.
 - o If year < year of first dose, then set month and day to December 31st.
 - o If year > year of first dose, then set month and day to January 1st.
- If month and year are present and day is missing:
 - If year=year of first dose and
 - ❖ if month = month of first dose then set day to day of first dose date.
 - ❖ if month < month of first dose then set day to last day of month.
 - ❖ if month > month of first dose then set day to 1st day of month.
 - o if year < year of first dose then set day to last day of month.
 - o if year > year of first dose then set day to 1st day of month.
- For all other cases, set onset date to date of first dose.

Concomitant Medications/Medical History

- If start date is completely missing, start date will not be imputed.
- If (year is present and month and day are missing) or (year and day are present and month is missing), set month and day to January 1.
- If year and month are present and day is missing, set day to 1st day of month.

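### Four adverse event rules in SAP Appendix A impute onset to first dose without checking the stop date, so an event that ended before treatment can be counted as treatment-emergent

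*SAP*

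**What the plan says.** SAP Appendix A has four adverse event branches that end at the first-dose date:

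- Onset wholly missing: "If onset date is completely missing, onset date is set to date of first dose".
- Month missing, with or without a recorded day: "If year = year of first dose, then set month and day to month and day of first dose".
- Only the day missing, in the year of first dose: "if month = month of first dose then set day to day of first dose date".
- Remaining patterns: "For all other cases, set onset date to date of first dose".

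Partial onsets in an earlier period are treated differently. For a missing month, for instance: "If year < year of first dose, then set month and day to December 31st". An onset in an earlier month of the first-dose year goes to the last day of that month.

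SAP section 8 gives the imputed date its role: "For the purpose of calculating treatment emergence and inclusion in summary tables, incomplete onset dates will be imputed as detailed in Appendix A". Its date test for emergence is that the event "occurs on or after Cycle 1/Day 1 and through the end of the study", so an onset equal to the first-dose date qualifies.

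Protocol 12.4 sets the intended handling of earlier events: "AEs that occur after informed consent but before first dosing of study medication will not be summarized but will be listed". Both documents also have routes to TEAE status that do not rest on a new onset after dosing. An event present before dosing counts if it worsens or is later judged treatment-related, and the protocol adds any treatment-related event whatever its start date.

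**The concern.** Using first dose as the default is a sensible precaution when nothing shows whether an event began before or after treatment. A stop date before first dose does show it: the event was over before any study drug was given. The four branches ignore that information, and the imputed onset then contradicts a recorded date.

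Such records can exist. The assessment schedule (Table 2) has adverse event evaluation at screening. Protocol 12.5.1 records events before treatment assignment that are tied to protocol-mandated interventions, and Protocol 12.6.2 takes serious events from consent.

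The SAP already uses this kind of check elsewhere. SAP 5.6 uses stop dates to separate prior from concomitant medications. In Appendix A, the rule for a missing day of death or progression prevents the imputed date from falling before the last assessment. Adverse event onset has no comparable check. At stake is whether the TEAE summaries contain only what Protocol 12.4 intends.

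**Working it through.** The plan gives no figure to reproduce. The check is to apply the Appendix A rules as written to example records.

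**Assumed inputs.** First dose 20 March 2016. Recorded stop date 10 March 2016, except in the last row, where it is 1 June 2015. The event did not worsen and was not judged treatment-related.

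**Rules.** Impute onset by Appendix A. The event is emergent by date if imputed onset ≥ first dose (SAP section 8). The dates are inconsistent if imputed onset > stop date.

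| Recorded onset | Branch | Imputed onset | TEAE by date | Onset after stop |
|---|---|---|---|---|
| nothing | completely missing | 20 Mar 2016 | yes | yes |
| 2016 only | month missing, same year | 20 Mar 2016 | yes | yes |
| 2016 and day 5, no month | month missing, same year | 20 Mar 2016 | yes | yes |
| March 2016 | day missing, same month | 20 Mar 2016 | yes | yes |
| March, day 5, no year | all other cases | 20 Mar 2016 | yes | yes |
| February 2016 | day missing, earlier month | 29 Feb 2016 | no | no |
| 2015 only | month missing, earlier year | 31 Dec 2015 | no | yes |

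In the first five rows, onset minus stop is 20 − 10 = 10 days and the event enters the TEAE summaries. The last row is not emergent by date, but its onset still falls after resolution, so a cap is useful there too.

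**With the cap.** If onset may not be later than the known stop date, the first five rows become 10 March 2016 or earlier, and none is a TEAE by date.

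**How often a branch would be reached, given the missing pattern.** This is an illustration only. Assume true onset is uniform over the 21 days before first dose (the length of the screening window in Table 2), so the mean gap is (1 + 21)/2 = 11 days, and that first dose is uniform over the calendar.

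- Wholly missing: 100%.
- Month missing: chance of the same year ≈ 1 − 11/365.25 = 97%.
- Day missing: chance of the same month ≈ 1 − 11/30.4 = 64%.

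These are chances that two dates share a calendar period. They are not misclassification rates, which also depend on how often the onset is incomplete and how often a stop date before first dose is recorded. The documents give neither.

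**The case against.** The strongest defence is that the affected pool is narrow and the default errs towards over-counting. Protocol 12.5.1 starts general adverse event recording at Cycle 1 Day 1. Before that, the text specifies only procedure-related events and serious events. Serious events are reported within 24 hours with investigator sign-off, which makes a missing onset less likely. Protocol 11.2 plans routine review for missing data and anomalies, and SAP section 10 plans source verification and electronic and manual checks. All of this stands as a limit on size. None of it changes the imputation rule for a date that stays incomplete, and caution has no purpose once the stop date settles the order.

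A reader might infer more than the documents support:

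- *Every incomplete onset goes to first dose.* It does not. Partial dates in an earlier year, or an earlier month of the same year, are imputed before first dose.
- *Every TEAE table is contaminated.* The serious, Grade 3 or higher, related and discontinuation tables each need a further attribute. A mild, unrelated screening event would reach only the overall and by-relationship summaries.
- *Reported durations or infusion-day patterns are distorted.* SAP section 8 plans no duration or day-of-onset summary. SAP 4.2 defines days since dose for listings, but nothing says listings carry the imputed onset.
- *One arm is favoured.* The rule is the same in both arms, both start study drug on Day 1, and randomization falls on Days -7 to 0, so most of the screening window precedes assignment. SAP section 7 also states that no safety outcome is pre-specified.

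**Conclusion.** The point holds in a limited form. In four named branches, a record with an incomplete onset and a stop date before first dose becomes treatment-emergent by date, contrary to Protocol 12.4. The result is certain whenever such a record occurs, and nothing elsewhere in either document corrects it.

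The number of records is unknown and probably small. No difference between arms is shown and efficacy is not touched. This is a minor drafting correction. The conclusion assumes that the adverse event form captures a stop date, which the documents do not describe field by field, and that the event does not qualify as a TEAE through worsening or relatedness.

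**What to change.** Add to the adverse event rules in SAP Appendix A:

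> If the available stop-date information shows that the event ended before first dose, onset is imputed no later than the stop date and the event is not treatment-emergent by date. Events that the protocol treats as emergent because they are treatment-related or worsened are unaffected. In all other branches the imputed onset may not be later than a known stop date.

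Keep the first-dose default when the stop date is missing, does not settle the order, or is on or after first dose.

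The cost is one rule and one program check. Appendix A has no rule for adverse event end dates, so the text must also say how a partial stop date is read: for example, a stop month wholly before the month of first dose settles the order, while a stop in the same month with no day does not. No new data are needed if stop dates are already collected. SAP section 2 allows revision before database lock. After lock, SAP 4.5 would have the change documented in the clinical study report.
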